6.4.3 Day 2 (Day After Dosing) of Cycle 1 and Cycle 3 Only

- Record AEs and SAEs (Section 7.6) – may be collected by telephone.
- Record concomitant medications – may be collected by telephone.
- A single rovalpituzumab tesirine PK draw will be obtained 24 hours (\pm 2 hours) after start time of infusion of rovalpituzumab tesirine on Day 1.

6.4.4 Days 8 and 15 Visits (\pm 2 days) of Cycle 1 and Cycle 3

The following assessments will be performed at Cycle 1 (Day 8), Cycle 1 (Day 15), Cycle 3 (Day 8) and Cycle 3 (Day 15) (\pm 2 days):

- Physical examination (Section 7.7.1)
- Vital signs (Section 7.7.2)
- Urinalysis (Section 7.7.3)

- Fluid Retention Questionnaire with daily weight diary accountability (Section 7.7.7)
- Record AEs and SAEs (Section 7.6)
- Record concomitant medications
- Serosal fluid collection, if applicable (Section 7.4.9)
- Blood sample collection for:
 - CBC with differential (Section 7.7.3)
 - Serum chemistries (Section 7.7.3)
 - Rovalpituzumab tesirine PK

6.4.5 Washout Period Safety Assessments

After the last dose of ipilimumab has been administered on Cycle 5 Day 1 in Cohorts 2 and 3, the subject will undergo a washout period for 6 weeks if in Cohort 2, and 8 weeks if in Cohort 3. During the washout period, subjects will have a Safety Visit in clinic and telephone follow-up calls as described in Table 3 and Table 4.

Table 3. Cohort 2 Washout Period Schedule

Study Drug	Cycle 5 Day 1	Washout Period						Cycle 6 Day 1 ^b
		Week 1	Week 2 ^a	Week 3	Week 4 ^a	Week 5		
Nivolumab 1 mg/kg	X		Safety Visit		Phone Follow-up			
Ipilimumab 1 mg/kg	X							
Nivolumab 480 mg q4wk				X				

- a. Window for visit/telephone follow-up is ± 3 days.
 b. Window for visit is ± 2 days.

Table 4. Cohort 3 Washout Period Schedule

Study Drug	Cycle 5 Day 1	Washout Period							Cycle 6 Day 1 ^b
		Week 1	Week 2 ^a	Week 3	Week 4 ^a	Week 5	Week 6 ^a	Week 7	
Nivolumab 1 mg/kg	X		Safety Visit		Phone Follow Up Visit		Safety Visit		
Ipilimumab 3 mg/kg	X								
Nivolumab 480 mg q4wk				X					

- a. Window for visit/telephone follow-up is ± 3 days.
 b. Window for visit is ± 2 days.

Safety Visit

The following will be performed during the Safety Visit:

- Physical examination (Section 7.7.1)
- Vital signs (Section 7.7.2)
- ECOG performance status (Appendix 13.3)
- Record AEs and SAEs (Section 7.6)
- Record concomitant medications
- Blood samples for:
- CBC with differential (Section 7.7.3)
- Serum chemistries (Section 7.7.3)

Telephone Follow-up Calls

The following will be reviewed during the telephone follow-up call:

- Any new or ongoing AEs
- Any new concomitant medications

6.4.6 Efficacy Assessment and Tumor Response

On applicable cycles, disease assessment will occur at least 3 days, but no greater than 7 days, prior to day of dosing.

Cohort 1 Imaging Schedule:

- Prior to Cycle 3 Day 1 (6 weeks after Screening imaging)
- Prior to Cycle 5 Day 1 (7 weeks after Cycle 3 Day 1 imaging)
 - If response is noted (CR or PR) on Cycle 5 Day 1 scan, a mandatory 4 week follow up scan will be performed to confirm response. The 4 week follow up scan may be omitted if no response is noted on Cycle 5 Day 1 scan.
- Prior to Cycle 7 Day 1 (8 weeks after Cycle 5 Day 1 imaging)
- After Cycle 5 Day 1, imaging will be collected every 8 weeks (at least 3 days, but no greater than 7 days, prior to day of dosing) during the maintenance therapy stage of the study.

Cohort 2 Imaging Schedule:

- Prior to Cycle 3 Day 1 (6 weeks after Screening imaging)
- Prior to Cycle 5 Day 1 (6 weeks after Cycle 3 Day 1 imaging)

- Prior to Cycle 6 Day 1 (6 weeks after Cycle 5 Day 1 imaging given washout period)
- Prior to Cycle 8 Day 1 (8 weeks after Cycle 6 Day 1 Imaging)
- After Cycle 8 Day 1, imaging will be collected every 8 weeks (at least 3 days, but no greater than 7 days, prior to day of dosing) during the maintenance therapy stage of the study.

Cohort 3 Imaging Schedule:

- Prior to Cycle 3 Day 1 (6 weeks after Screening imaging)
- Prior to Cycle 5 Day 1 (6 weeks after Cycle 3 Day 1 imaging)
 - If response is noted (CR or PR) on Cycle 5 Day 1 scan, a mandatory 4 week follow up scan will be performed to confirm response. The 4 week follow up scan may be omitted if no response is noted on Cycle 5 Day 1 scan.
- Prior to Cycle 6 Day 1 (8 weeks after Cycle 5 Day 1 imaging given washout period)
- Prior to Cycle 8 Day 1 (8 weeks after Cycle 6 Day 1 imaging)
- After Cycle 8 Day 1, imaging will be collected every 8 weeks (at least 3 days, but no greater than 7 days, prior to day of dosing) during the maintenance therapy stage of the study.

Disease assessment will consist of the following:

- CT scans of the chest, abdomen, and pelvis (and neck if indicated) (Section 7.2)
- MRI of the brain – if clinically indicated (e.g. if CNS progression has been documented previously). CT of the brain with IV contrast may be substituted at the discretion of the study doctor.

Tumor response will be determined and categorized by RECIST v1.1 (Eisenhauer, 2009).

6.5 End of Treatment Visit

The EOT Visit occurs within 7 days of documentation of the decision to discontinue treatment. The following procedures will be performed at the EOT Visit:

- Physical examination (Section 7.7.1)
- Vital signs (Section 7.7.2)
- Urinalysis (Section 7.7.3)
- Pregnancy test (urine) (Section 7.7.3) for women of childbearing potential
- Triplicate ECG (Section 7.7.4)

- Echocardiogram (Section 7.7.5)
- ECOG performance status (Appendix 13.3)
- Record AEs and SAEs (Section 7.6)
- Fluid Retention Questionnaire with daily weight diary accountability (Section 7.7.7) if EOT occurs prior to Cycle 5
- Record concomitant medications
- Disease assessment consisting of CT scans of the chest, abdomen, and pelvis (and neck if indicated) – may be omitted if a Disease/Response Assessment was performed within the last 6 weeks (Section 7.2)
- MRI of the brain – if clinically indicated (e.g., if CNS progression has been documented previously); may be omitted if a Disease/Response Assessment was performed within the last 6 weeks. CT of the brain with IV contrast may be substituted at the discretion of the investigator (Section 7.2).
- Blood samples for:
 - CBC with differential (Section 7.7.3)
 - Serum chemistries (Section 7.7.3)
 - Coagulation tests (Section 7.7.3)
 - Rovalpituzumab tesirine PK and ATA
 - Nivolumab PK and ATA
 - Ipilimumab PK and ATA
 - Blood ██████████ (Section 7.4.2)
 - Plasma for ctDNA (Cycle 1 Day 1, pre-dose only) sample
 - Blood soluble markers (Section 7.4.3)
 - Flow Cytometry (Section 7.4.4)
 - Peripheral blood RNA (Section 7.4.5)
 - CTCs (Section 7.4.6)
 - Endocrinology Tests, including ACTH, thyroid stimulating hormone (TSH), and free thyroxine (T4)
- (Optional) fresh tumor tissue, collected at disease progression (Section 7.4.1)
- Serosal fluid, if applicable (Section 7.4.9)

6.6 Long-Term Follow-up; Every 6-12 weeks \pm 1 week

For all subjects who discontinue study drugs for reasons other than disease progression (e.g. due to an AE), the first follow-up visit will occur at 6 weeks (\pm 1 week) after the last dose of study drugs, then q6wk (\pm 1 week) until 6 months, then q12wk (\pm 1 week) until disease progression, initiation of new anticancer therapy, or withdrawal/ termination from the study. Procedures to be conducted on follow-up visits include:

- Record AEs and SAEs (Section 7.6)
- Disease response assessment consisting of CT scans of the chest, abdomen, and pelvis (and neck if indicated) (Section 7.2)
- MRI of the brain – if clinically indicated (e.g. if CNS progression has been documented previously). CT of the brain with IV contrast may be substituted at the discretion of the investigator (Section 7.2).
- (Optional) fresh tumor tissue, collected at disease progression (Section 7.4.1)
- Blood samples for:
 - Blood soluble markers (Section 7.4.3)

Survival status will be followed until death or study withdrawal/termination, whichever occurs first.

At progression, an optional collection of fresh tumor tissue may be conducted (Section 7.4.1).

After disease progression, subjects who are not retreated will be followed for subsequent anticancer therapies and dates, as well as survival status, q6wk (\pm 1 week) for 24 weeks (6 months), then q12wk (\pm 1 week) until death or study termination, whichever occurs first.

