7.6 Adverse Event Collection

All AEs reported from the time of study drug administration until 100 days following discontinuation of study drug administration will be collected, whether solicited or spontaneously reported by the subject. In addition, protocol-related serious and non-serious AEs will be collected from the time the subject signed the study-specific informed consent.

Serious and non-serious AEs occurring after the study-specific informed consent is signed but prior to the initial dose of study drug will be collected **only** if they are considered by the investigator to be causally related to the study-required procedures.

AE information will be collected as shown in [Figure 2](#).

Figure 2. Adverse Event Collection

*Only if considered by the investigator to be causally related to study-required procedures.

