			Day -14 to -1	Day -1		Day 1 (±2 d)	Day 2 ¹	Day 8 ³ (±2 d)	Day 15 ³ (±2 d)			
	Circulating Tumor Cells ⁴⁴					X ⁴⁵					X	
	Genotyping ⁴⁶		X									
	Serosal Fluid ⁴⁷					X		X		X		
	Cell Free Circulating Tumor DNA (ctDNA) ⁴⁸					X					X	

Table Notes

* **Cycles 1 – 3 are 3 weeks. Cycles 4 and beyond are 4 weeks.**

- 1) Only applies to Cycle 1 and Cycle 3 when rovalpituzumab tesirine is administered.
- 2) EOT occurs within 7 days of documentation of the decision to discontinue treatment.
- 3) Visits on Days 8 and 15 should be done during Cycles 1 and 3 only (may be omitted during cycles that do not include rovalpituzumab tesirine).
- 4) LTFU includes the 100 day follow up for safety; LTFU also occurs q6wk (±1 week) until 6 months, then q12wk (±1 week) until disease progression, initiation of new anticancer therapy, or withdrawal/termination from the study. Disease/Response Assessment consists of subsequent anticancer therapies and dates, date of progression (if not already captured on study), and survival status. Subjects will be followed for survival until death or study termination, whichever occurs first. After disease progression, subjects who are not retreated will be followed (Section 6.6).
- 5) This may be a telephone follow-up or performed in clinic.
- 6) Prescreening ICF only.
- 7) Informed consent for the main portion of this study will be obtained prior to the performance of any study procedures and may occur within 30 days prior to the Day 1 Visit. All other screening procedures must occur within 14 days prior to Day 1.
- 8) Confirmation of study eligibility per inclusion/exclusion criteria.
- 9) Medical and Surgical History includes descriptions of conditions or procedures, and dates of onset - offset.
- 10) Malignancy History includes tumor type, stage, sites of metastases, mutational status.
- 11) Prior Anticancer Treatments include names of specific treatments, dates of administration, response to therapy, and DOR, if known.

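### Section 6.6 schedules AE recording after the EOT visit only for subjects who stop for reasons other than progression, although the 100-day AE window covers everyone

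*Combined protocol and SAP*

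**What the plan says.** **The window is universal.** Section 7.6 states: "All AEs reported from the time of study drug administration until 100 days following discontinuation of study drug administration will be collected". Section 8.1.1.1 uses the same 100 days to define a TEAE, and Section 8.2.2.6 uses it as the safety reporting period. None of the three makes an exception for progression. Section 8.2.2.1 has AEs elicited by open questioning at study visits.

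**The visits are not universal.** The EOT visit (Section 6.5) records AEs for everyone, within 7 days of the documented decision to stop. After that, Section 6.6 provides: "For all subjects who discontinue study drugs for reasons other than disease progression (e.g. due to an AE), the first follow-up visit will occur at" a nominal 6 weeks (1 week either way), with the clock and interval given as "after the last dose of study drugs, then q6wk" until 6 months. Recording AEs and SAEs is the first procedure listed. These visits end at progression or new anticancer therapy. For the other group, Section 6.6 states: "After disease progression, subjects who are not retreated will be followed for subsequent anticancer therapies and dates, as well as survival status, q6wk" for 24 weeks and 12-weekly thereafter. AEs are not listed there.

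**The appendix and Section 4.3 lean the other way.** All three schedules in Appendix 13.1 mark AEs in the LTFU column. Their notes (note 4 for Cohort 1, note 5 for Cohorts 2 and 3) say: "LTFU includes the 100 day follow up for safety". The same notes refer follow-up after progression back to Section 6.6. Section 4.3 asks for EOT and LTFU safety data from anyone who withdraws from treatment, if possible, and also cites Sections 6.5 and 6.6.

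**The concern.** Safety is the primary objective (Section 2.1), and TEAE incidence by cohort is one of its main summaries (Section 10.3.5.1). Section 3.1 also asks the SMC to look for safety concerns that emerge beyond the DLT window. If AEs are asked about after EOT only in subjects who stopped for something other than progression, ascertainment depends on the subject's outcome. Reported incidence could then be too low, and the shortfall would be larger in a cohort where more subjects stop for progression. A difference between cohorts could arise partly from how often people were asked.

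**Working it through.** The 100 days is a design choice, stated alike in Sections 7.6, 8.1.1.1 and 8.2.2.6, so there is no figure to re-derive. The check is a calendar count against it. Day 0 is taken as the last dose, the clock Section 6.6 uses for its visits. The protocol does not say which date counts as discontinuation of study drug.

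**1. Scheduled AE contacts after EOT, within 100 days**

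- Stopped for another reason: weeks 6, 12 and 18 are 6 × 7 = 42, 12 × 7 = 84 and 18 × 7 = 126. With ±7 days these become 35–49, 77–91 and 119–133. Two visits fall inside the window; the third is outside even at its earliest.
- Stopped for progression: none listed, although six-weekly contacts take place.
- Neither group has a dated contact at day 100. In the first group the nominal schedule leaves 100 − 84 = 16 days at the end.

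**2. Length of the interval without a scheduled AE contact after progression**

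Inputs: scans 3–7 days before the next dosing day (Section 6.4.6); dosing intervals of 21 or 28 days and washouts of 42 days (Cohort 2) or 56 days (Cohort 3) after Cycle 5 Day 1 (Table 2); EOT 0–7 days after the decision (Section 6.5). Assumption: the decision to stop is made on the day of the scan.

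Earliest EOT = interval − 7. Latest EOT = interval − 3 + 7. Days remaining = 100 − EOT day.

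| Interval (days) | Scan day | EOT day | Days left to day 100 |
|---|---|---|---|
| 21 | 14–18 | 14–25 | 75–86 |
| 28 | 21–25 | 21–32 | 68–79 |
| 42 (Cohort 2 washout) | 35–39 | 35–46 | 54–65 |
| 56 (Cohort 3 washout) | 49–53 | 49–60 | 40–51 |

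Outside the washouts the range is 68 to 86 days.

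**3. Direction of the effect (illustration only)**

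Let f be the share stopping for progression, and s the capture of post-EOT TEAEs without a scheduled AE contact relative to capture with one. Neither is in the documents. Assuming full capture in the other group and equal risk in both, captured share = (1 − f) + f × s.

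- f = 50%, s = 75%: 0.5 + 0.5 × 0.75 = 87.5%.
- f = 90%, s = 50%: 0.1 + 0.9 × 0.5 = 55%.

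Two cohorts with the same true post-EOT risk q but f of 50% and 90% would differ by q × 0.4 × (1 − s). With q assumed to be 20%, that is 0.2 × 0.4 × 0.25 = 2 points to 0.2 × 0.4 × 0.5 = 4 points. With q from 10% to 30%, the range is 1 to 6 points.

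**The case against.** The strongest reply is that the protocol already requires what is said to be missing. The schedules mark AEs under LTFU. Their notes place a 100-day safety follow-up inside LTFU with no limit by reason for stopping. Section 4.3 seeks LTFU safety data from anyone who withdraws from treatment, Section 8.1 has the investigator monitor AEs routinely throughout the study, and Section 8.2.2.6 follows non-serious AEs through the reporting period. On this view Section 6.6 is merely incomplete wording.

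Much of that stands, and it rules out some stronger readings:

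- A reader might infer that subjects who stop for progression are never asked about AEs, so that only spontaneous reports arrive. The documents do not support this: the intention to follow everyone is plain, and the EOT visit covers all. The gap is in dated solicitation, not in the duty to collect.
- A reader might subtract 7 from 100 and infer 93 uncovered days. The 7 days run from the decision to stop, and the 100 from discontinuation of study drug. The subtraction works only if those share a start date, which the protocol does not say. The EOT column header does refer to 7 days from last dose, but its own note counts from the decision, and on the timings above progression is seen at day 14 or later.
- A reader might apply the gap to every subject who stops for progression. Retreated subjects repeat the full schedule with AE recording (Sections 3.1.2 and 6.1), and some subjects may die before day 100.
- The contrast is not wholly clean: subjects who stop for other reasons also lose their AE visits once they progress or start new therapy.

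The objection does not supply a dated AE contact after progression. The appendix notes and Section 4.3 both send the reader back to Section 6.6, the section that omits AEs for this group. A site following it literally would make the six-weekly contact without asking about AEs.

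**Conclusion.** The concern holds as an internal inconsistency with a practical consequence. The duty to collect AEs to 100 days covers all subjects, while the only dated AE visits after EOT depend on the reason for stopping. Followed literally, Section 6.6 gives two scheduled contacts against none. For a subject who stops for progression at an on-treatment scan, the interval without one is roughly 68–86 days, or 40–65 days after a washout. This rests on counting from last dose and deciding on the day of the scan.

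The effect on TEAE incidence cannot be estimated from the documents, which give neither the share stopping for progression nor the capture rate without a contact. The 1 to 6 points above show direction under assumed values and nothing more. The summaries affected are descriptive, with no consequence for type I error, power or sample size. A reader might infer that cohort expansion is compromised. It is largely unaffected, because DLTs are assessed over the first 12 weeks of treatment. The exception is a subject who stops at the scan before Cycle 3 Day 1 and could lose scheduled questioning for part of that period.

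**What to change.** In Section 6.6 and Appendix 13.1, state one AE contact schedule through day 100 after discontinuation of study drug. It should apply to all treated subjects, whatever the reason for stopping and whether or not progression or new therapy occurs. In practice:

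- add recording of AEs and SAEs to the existing six-weekly contacts, timed from last dose so that weeks 6 and 12 fall inside the window for everyone (contacts now described as following progression need not fall there);
- add one telephone contact at about day 100, since the next nominal visit after day 84 is day 126;
- say which date counts as discontinuation of study drug, so that the 100-day window and the visit schedule share a clock.

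The cost is a few minutes of site time per contact and one extra call per subject.

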2.4 Endpoints

2.4.1 Safety Endpoints

Analyses of the safety endpoints will include the following measurements or assessments:

- Adverse Events (AEs) and Dose-Limiting Toxicities (DLTs)
- Vital signs (Section 7.7.2)
- Body weight (Section 7.7.2)
- Laboratory abnormalities (Sections 7.7.3 and 8.3.7)
- Electrocardiographic parameters (e.g. QT interval corrected for heart rate [QTc], QT interval corrected for heart rate by Fridericia's formula [QTcF]) (Section 7.7.4)
- Echocardiography (Section 7.7.5)
- Eastern Cooperative Oncology Group (ECOG) performance status (Section 7.7.6)
- Monitoring of concomitant medications

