5.7 Prior and Concomitant Therapy

Any medication or vaccine (including over-the-counter or prescription medicines, vitamins and/or herbal supplements) that the subject is receiving at the time of enrollment, or receives during the study, must be recorded along with the reason for use, date(s) of administration including start and end dates, and dosage information including dose, route and frequency.

Any concomitant therapy given for a study protocol-related AE should be recorded from the time of informed consent.

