6.1 Enrollment

Subjects who provide informed consent will be screened for eligibility. Once screening procedures have been completed, and for those subjects who meet all of the entry criteria, a Registration and Enrollment Form will be completed and submitted to the sponsor or designee to confirm eligibility. Approved subjects will then be enrolled into a treatment cohort. Refer to the Study Binder for the enrollment form, contact numbers, and other details of enrollment.

Safety assessments (Section 2.4.1) will include physical examinations, vital signs, body weight, ECOG performance status, AE assessments, laboratory tests (Section 7.7.3), ECGs, echocardiograms, Fluid Retention Questionnaire, concomitant medications, AEs, and concomitant therapies will be recorded from Day 1 (pre-dose) through the safety reporting period. At the same time, subjects will maintain a diary of daily weights. Any protocol-related AE should be recorded from the time of informed consent as well as any concomitant therapies given for treatment of the AE.

Study activities are listed by visit in this section and descriptions of all study assessments are presented in Section 7. A schedule of events is provided in Appendix 13.1.

Subjects undergoing retreatment as described in Section 3.1.2 will follow the same study schedule from Screening through EOT and LTFU.

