8.1.1 Definitions

8.1.1.1 Adverse Event

An AE is defined as any untoward medical occurrence in a patient or clinical investigation subject administered a pharmaceutical product and which does not necessarily have a causal relationship with this treatment. An AE can therefore be any unfavorable and unintended sign (including an abnormal laboratory finding), symptom, or disease temporally associated with the use of a medicinal (investigational) product, whether or not the event is considered causally related to the use of the product.

Such an event can result from use of the drug as stipulated in the protocol or labeling, as well as from accidental or intentional overdose, drug abuse, or drug withdrawal. Any worsening of a pre-existing condition or illness is considered an AE. Worsening in severity of a reported AE should be reported as a new AE. Laboratory abnormalities and changes in vital signs are

considered to be adverse events only if they result in discontinuation from the study, necessitate therapeutic medical intervention, and/or if the investigator considers them to be AEs.

An elective surgery/procedure scheduled to occur during a study will not be considered an AE if the surgery/procedure is being performed for a pre-existing condition and the surgery/procedure has been pre-planned prior to study entry. However, if the pre-existing condition deteriorates unexpectedly during the study (e.g., surgery performed earlier than planned), then the deterioration of the condition for which the elective surgery/procedure is being done will be considered an AE.

All protocol-related AEs must be collected from the signing of the study specific informed consent until study drug administration.

In addition, adverse events with onset or worsening reported by a subject from the time that the first dose of study drug is administered until 100 days have elapsed following discontinuation of study drug administration will be considered as treatment-emergent adverse events.

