8.2.2.6 Reporting Periods for Adverse Events and Serious Adverse Events

The safety reporting period for all AEs and SAEs is from the time of study drug administration (Cycle 1 Day 1) until 100 days following discontinuation of study drug administration. In addition, protocol related serious adverse events and protocol-related nonserious adverse events will be collected from the time the subject signed the study-specific informed consent, only if considered by the Investigator to be causally related to study-required procedures. All SAEs that occur after the safety reporting period and are considered study treatment-related in the opinion of the investigator should also be reported to the sponsor or designee.

Each SAE must be followed until the SAE returns to baseline (resolves or recovers to baseline) or the SAE stabilizes (resolves or recovers with sequelae); the SAE is considered not recovered or not resolved by the investigator; or the subject dies (the SAE end date is equal to the date of death). SAE outcome may not be possible to collect when a subject withdraws consent.

Additionally, all SAEs that occur *after* the safety reporting period (as defined above) that are considered study treatment-related by the investigator, should also be reported to the sponsor or its designee.

All non-serious AEs will be followed through the safety reporting period.

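### Section 6.1 requires concomitant medications to be recorded for 100 days after discontinuation, but the Section 6.6 follow-up list and the LTFU columns of Appendix 13.1 drop them after the End of Treatment visit

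*Combined protocol and SAP*

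**What the plan says.** Four parts of the protocol set the duty and its length.

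- Section 6.1: "concomitant medications, AEs, and concomitant therapies will be recorded from Day 1 (pre-dose) through the safety reporting period".
- Section 8.2.2.6 defines that period and counts its end from the stopping of study drug: "The safety reporting period for all AEs and SAEs is from the time of study drug administration (Cycle 1 Day 1) until 100 days following". Section 7.6 uses the same limit for collection ("All AEs reported from the time of study drug administration until 100 days following discontinuation of study drug administration will be collected"), and Section 8.1.1.1 uses it to define treatment-emergent AEs (TEAEs).
- Section 5.7 separately says that any medication the subject "receives during the study, must be recorded along with the reason for use", with dates, dose, route and frequency.
- Section 2.4.1 lists "Monitoring of concomitant medications" among the safety endpoints, and Section 10.3.5.7 gives it an incidence table by cohort. That section states no time window.

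The operational parts read differently. Section 6.5 lists concomitant medications at EOT. Section 6.6, under "Procedures to be conducted on follow-up visits include", lists AE and SAE recording, CT, brain MRI if indicated, optional tissue and blood soluble markers. In the three cohort schedules of Appendix 13.1 the AE row has a mark under LTFU, while the concomitant-medication row ends at EOT. The footnote to the LTFU column nevertheless says that the column covers the 100-day safety follow-up.

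**The concern.** A site normally works from the visit list and the grid. Read that way, medication recording ends at EOT while AEs go on counting as treatment-emergent to day 100. A site that works from Sections 5.7 and 6.1 would continue. Each complies with part of the protocol, so the length of the medication record would depend on which part the site follows.

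Safety is the primary objective and concomitant medication is a named safety endpoint. The data at risk are the treatments given for late events. Appendix 13.7 calls corticosteroids a primary therapy for immuno-oncology drug-related events, and the protocol refers repeatedly to hormone replacement for endocrinopathies. The Section 10.3.5.7 table would be incomplete after EOT, and unevenly so across sites.

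**Working it through.** The plan gives no figure to reproduce on this point. The check has two parts: a comparison of the passages, and a count of the days affected.

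**1. Passages side by side**

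| Item after EOT | Sections 6.1, 5.7, 7.6, 8.2.2.6 | Section 6.6 list | LTFU column, Appendix 13.1.1 to 13.1.3 |
|---|---|---|---|
| AEs and SAEs | to day 100 | listed | marked |
| Concomitant medications | to day 100 (6.1); throughout the study (5.7) | not listed | not marked |

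The schedule tables are partly broken in the text available, but the Section 6.6 list confirms the omission independently.

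**2. Days affected**

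Inputs:
- Safety window W = 100 days (Sections 7.6 and 8.2.2.6), counted here from the last dose.
- EOT timing. The schedule header puts EOT within 7 days of the last dose. Section 6.5 and the schedule footnote put it within 7 days of the documented decision to stop. Both are carried through.
- d = days from last dose to the decision. The documents do not give d. I assume that the decision falls at the next planned dose, so d is 21 (3-weekly cycles), 28 (4-weekly cycles), 42 (Cohort 2 washout) or 56 (Cohort 3 washout, Section 5.1.1, Table 2).

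Formula: days after EOT = W − (d + 7). Under the schedule header, d = 0. EOT is taken on its latest permitted day, so each result is the smallest value for its case.

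| Case | EOT day | Days after EOT |
|---|---|---|
| Schedule header, d = 0 | 7 | 100 − 7 = 93 |
| 3-week gap | 21 + 7 = 28 | 100 − 28 = 72 |
| 4-week gap | 28 + 7 = 35 | 100 − 35 = 65 |
| 6-week gap | 42 + 7 = 49 | 100 − 49 = 51 |
| 8-week gap | 56 + 7 = 63 | 100 − 63 = 37 |

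If the window is counted from the decision date instead, the result is 93 days in every case. More than half the window is affected whenever EOT falls before day 50, which is every case except the 8-week washout.

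**3. Visits at which the data could be collected**

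Section 6.6 puts the first follow-up visit 6 weeks after the last dose and then every 6 weeks, each ±1 week. That gives day 42 (35 to 49) and day 84 (77 to 91) inside the window; the third is day 126. In the 6- and 8-week cases nominal day 42 falls before EOT, so only the day 84 visit follows it. None of these visits lists medication recording.

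**4. Subjects not reached by these visits**

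The Section 6.6 visits with AE recording are described for subjects who stop for reasons other than progression, and they end at progression or new anticancer therapy. After progression the section lists only later anticancer treatment and survival. Section 7.6 makes no such exception to the 100 days. For these subjects the visit list therefore omits AE recording as well.

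**The case against.** The best reply is that the duty is already stated twice, in Sections 5.7 and 6.1, and that the Section 6.6 list is not worded as exhaustive. On that view a missing bullet and grid mark is a drafting slip and not a decision to stop collecting. This is fair as to intent. It does not remove the conflict, because the schedules omit the item as well and their own footnote says that the LTFU column serves the 100-day safety follow-up. It is also right that days after EOT are not days of missing data: a medication already recorded at EOT has its start date on file, and some sites will continue under Section 6.1.

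Two stronger readings are tempting, and the documents do not support them.

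- A reader might infer that TEAEs themselves are under-recorded. Section 7.6 keeps collecting AEs to day 100, solicited or spontaneous, and Section 8.1 includes actions taken in the AE record. What may be lost is the dose, route and dates of treatment that Section 5.7 asks for.
- A reader might infer that the lack of safety laboratory tests at LTFU also contradicts Section 6.1. In that run-on sentence the recording clause most naturally governs medications, AEs and therapies. Section 7.7.3 ties laboratory timing to Appendix 13.1, which agrees with Section 6.6 in scheduling none. Nor does AE status depend on a scheduled test. Section 8.1.1.1 says laboratory changes are "considered to be adverse events only if they result in discontinuation from the study, necessitate therapeutic medical intervention", and then adds the investigator's own judgement as a further route. The absence of tests is at most a possible limit on detecting asymptomatic abnormalities, of unknown size.

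**Conclusion.** The contradiction on concomitant medications stands and should be resolved. Sections 5.7 and 6.1 require recording over a window in which Section 6.6 and all three schedules do not list it, and the result would be medication data for late TEAEs that are incomplete and differ by site.

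The part of the 100-day window affected is 93 days on the schedule header's definition of EOT, and 72, 65, 51 or 37 days for 3-, 4-, 6- or 8-week gaps. The last four rest on the assumption that the decision to stop is made at the next planned dose and EOT follows 7 days later. These figures measure the period without a scheduled medication entry. The amount of data actually lost depends on site practice and cannot be computed from the documents. The same section leaves AE recording unlisted for subjects who stop for progression.

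**What to change.** 1. Add to the Section 6.6 list: *Record concomitant medications (through 100 days after discontinuation)*.
2. Mark the LTFU column of the concomitant-medication row in Appendix 13.1.1, 13.1.2 and 13.1.3, with a footnote giving the same limit.
3. State in Section 10.3.5.7 that the table covers first dose to 100 days after discontinuation, so that it matches the TEAE window.
4. Reconcile Section 6.6 with Section 7.6 for subjects who stop for progression, so that AEs and concomitant medications are both collected to day 100 for them.

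For subjects already on the Section 6.6 visits this needs no new visit, only a little more data entry. For subjects who have progressed it needs a safety contact, which can sit within the 6-weekly follow-up for survival and later treatment that Section 6.6 already provides. No added laboratory test is needed to resolve this point.
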